 - Preterm birth before 30 weeks: rate of delivery before 29+6 weeks
 - Preterm birth before 28 weeks: rate of delivery before 27+6 weeks
 - Birth weight: median weight (g) of the newborns at birth
 - Fetal or neonatal death: rate of intrauterine demise or neonatal death during the first 24 hours
 - Neonatal morbidity: rate of major adverse neonatal outcomes before discharge from the hospital
 - Intraventricular Haemorrhage (IVH): grades III-IV
 - Retinopathy of prematurity
 - Respiratory Distress Syndrome (RDS): grades II-IV,
 - Need for ventilation > 72 h
 - Necrotising enterocolitis
 - Proven or suspected sepsis, antibiotics (>5 days)
 - Need (Duration in days) for neonatal special care (NICU)
 - Harm from intervention
- Mother:
 - Maternal death
 - Significant maternal adverse events (rate):
 - Heavy bleeding: bleeding that requires a medical intervention
 - Cervical tear: cervical rupture due to the pessary placement
 - Uterine rupture: rupture of the uterus due to contractions or surgery
 - Physical or psychological intolerance to pessary: discomfort or pain due to the pessary that makes daily life uncomfortable (number of cases)
 - Rupture of membranes before 32 weeks: rate of–rupture of amniotic membranes before 31+6 weeks

[figure not shown]
- Infection/inflammation
- Hospitalisation for threatened preterm labour before 32 weeks: requirement of hospitalisation due to preterm contractions that need medical treatment to try to stop them before 31+6 weeks (rate)
 - Mean hospital stay duration: number of days of admittance at the hospital
 - Use of tocolytic treatment: Type of tocolytic, days of treatment, dose

4.2. Description of the trial design.

Open Multicentre International Collaborative Randomized Controlled Trial, in parallel groups, based on intention-to-treat analysis comparing the placement of a prophylactic cervical pessary with usual management in twin pregnancies with shortened cervix ≤ 25 percentile

4.3. Flowchart.

4.4. Description of the medical device and the treatment regimen.

The cervical pessary is a vaginal device (silicone ring) that is used to treat pregnant women for preventing spontaneous preterm birth. This device can be easily placed around the uterine cervix without pain (see annex I).

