A medically qualified investigator will assess the relationship of AEs to the study medication.

All SAEs must be reported to the main investigator. He will perform an initial check of the report, request any additional information, and he will notify it to the Ethics Committee. All SAE information will be recorded. It may be appropriate that some SAEs do not require immediate reporting but this must be justified. Justification might be determined, for example, by admission to hospital, or prolongation of hospitalization, where this is to be expected in the underlying disease or condition.

All adverse events (AE) life-threatening or resulting in death will be notified within 24 hours. All AE that are not life-threatening will be notified within 15 days. The rest of AE will be recorded and analyzed at the end of the study.

9. Statistics

9.1. Description of statistical methods.

The primary statistical aim is to compare the primary combined outcome “long-term survival without neuro-developmental disability at 3 years follow up” with a two-sided Cochran-Mantel-Haenszel-Test and a significance level of $\alpha=0.05$. The primary outcome refers to a combined event in any of the twin and will be analysed for all pregnancies with available primary endpoint. The stratified study design is accounted by this stratified test according to the gestation groups.

The main statistical evaluation will be performed at two time points. (1) The complete data set for the secondary endpoints will be available after the last women enrolled in this study has delivered her twins, so the analysis of these outcome parameter will be done right after this event. (2) The primary outcome will be evaluated 3 years after the last woman enrolled in this study has delivered her twins.

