A descriptive analysis by preterm birth will be carried out calculating means and medians for quantitative variables and proportions with 95% confidence intervals for categorical variables. In general, statistical comparisons with the pessary arm and the control arms or other group comparisons for primary and secondary outcomes will be performed with stratified tests as well as comparisons in the gestation subgroups. Events will be analysed for each twin and for single children assuming appropriate random effect regression models. Further subgroup analyses regarding the cervical length will be performed (e.g. CL 15 to 25mm and below 15mm). All tests, see also examples in the synopsis, will be two-sided using a significance level of $\alpha=0.05$.

For the primary endpoint we expect to have a drop out rate of up to 25% due to the long follow-up time (3 years) of the study; but we do not expect to have lost data for the secondary endpoints because for these parameters the study has a short follow-up time till time to birth only.

An interim analysis shall be conducted on key safety parameters after birth of 300 twins: the following safety endpoints will be assessed by a one-sided test with $\alpha=1\%$

- on level of the neonates: rate of preterm birth, time to birth, birth weight, death, neonatal morbidity, harm of intervention
- and on the maternal level: rate of hospitalisation for threatened preterm labour < 32 weeks, rate of PRoM <32 weeks, rate of infection / inflammation, rate of physical or psychological intolerance to pessary, rate of SAR/SAE, death.

The trial will be terminated as negative if a disadvantage for the pessary-treatment can be found in one of these tests. To guarantee a high safety level the significance level is chosen more conservatively than in a Bonferroni correction.

All analysis will be carried out with SPSS® version 19.0 or later (IBM Company SPSS Inc. Headquarters, Chicago, Illinois, USA) and R version 3.2.3 or later (R Foundation for Statistical Computing, Vienna, Austria).

Primary Outcome	Statistical Test
Children`s Long-Term Survival without Neuro-developmental Disability (3-Years-follow up)	Cochran-Mantel-Haenszel-Test, using 3 strata according to WoG
Secondary Outcome	Statistical Test
Birth before 34 Weeks of Gestation	Cochran-Mantel-Haenszel-Test, Chi-Quadrat Test
Time to Birth	Cox-Regression
Birthweight	van Elteren Test, Wilcoxon-Mann-Whitney Test
Fetal / Neonatal Death	Cochran-Mantel-Haenszel-Test, Chi-Quadrat Test

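### Section 9.1 analyses the secondary outcomes at the last delivery although several run to hospital discharge, and seven gestational-age cut-offs fall one day short of their labels (minor; primary outcome unaffected)

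*Combined protocol and SAP*

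**What the plan says.** **Timing.** Section 9.1 sets two main analyses. For the first it says "The complete data set for the secondary endpoints will be available after the last women enrolled in this study has delivered her twins". On when that analysis is run, its wording is "so the analysis of these outcome parameter will be done right after this event". Later in 9.1, when explaining why no secondary data should be lost, it adds that "for these parameters the study has a short follow-up time till time to birth only". The primary outcome follows three years after the last delivery.

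**Outcome windows.** Section 4.1.2 lists "Neonatal morbidity: rate of major adverse neonatal outcomes before discharge from the hospital". The components include ventilation beyond 72 hours and sepsis with more than 5 days of antibiotics. Days of neonatal special care are listed as well.

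**Interim.** Section 9.1 also says: "An interim analysis shall be conducted on key safety parameters after birth of 300 twins". Neonatal morbidity is among the items tested, and "The trial will be terminated as negative if a disadvantage for the pessary-treatment can be found in one of these tests". No data cut is given.

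**Cut-offs.** Section 4.1.2 labels five preterm-birth outcomes by 37, 34, 32, 30 and 28 weeks. It defines them as delivery before 36+6, 33+6, 31+6, 29+6 and 27+6. Membrane rupture and hospitalisation for threatened preterm labour, both labelled by 32 weeks, are also cut at 31+6.

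**The concern.** An outcome observed until discharge cannot be complete at birth. An analyst who follows 9.1 to the letter would lock the data while some infants are still in hospital. Those infants would have shortened special-care durations, and any morbidity item not yet decided would be missing or counted as absent. They are mainly the infants born early, in whom these items matter most.

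The same question is more consequential at the interim, because a single unfavourable test there ends the trial.

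The cut-offs leave a programmer with two rules for one outcome. A delivery on day 33+6 is before 34 weeks by the label but not before 33+6 by the definition.

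**Working it through.** The plan gives no figure for this point. Its sample size (500 evaluable, 672 recruited; section 9.2) concerns the primary outcome and does not depend on these windows. Here 672 serves only as a count of pregnancies.

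**1. Windows against the trigger**

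| Item in 4.1.2 | Earliest time it is settled | Known at delivery? |
|---|---|---|
| Gestational age at birth, birth weight | birth | yes |
| Ventilation > 72 h | more than 72 h after birth, if present | no |
| Antibiotics > 5 days | more than 5 days after birth, if present | no |
| Morbidity before discharge | discharge, if absent | no |
| Days of special care | end of that care | no |

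The schedule in 7.2 has a postnatal evaluation but gives it no date. The flowchart in 4.3 is not visible in the copy reviewed, so that absence carries little weight.

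**2. How many infants would be in hospital (simulation)**

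I read the last enrolled woman's delivery as the point when all enrolled women have delivered. The text should say so, because the last woman enrolled need not be the last to deliver.

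Inputs:
- 672 women enrolled evenly over 24 or 30 months (assumed). The calendar runs 66 months from July 2018 to December 2023; less 36 months of follow-up, this leaves about 30.
- Entry uniform over 16 to 28 weeks; 9.2 assumes three equal strata.
- Delivery age normal, conditional on entry, capped at 38.5 weeks (assumed). Lower case: 56.6% before 37 weeks and 11.3% before 32 (US twins, section 2.1). Higher case: 28.6% before 32 weeks (section 2.1, the comparison group of the case-control study) with 70% before 37 (assumed).
- Infants born before 34 weeks go home at 36 or 40 weeks postmenstrual age, others at birth (assumed).

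Mean number of pregnancies with infants in hospital:

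| Data taken at | Delivery rates | Number | Share |
|---|---|---|---|
| All delivered | all cases | 0.1 to 2.9 | 2.9/672 = 0.43% at most |
| Interim trigger | lowest case | 5.7 | 5.7/300 = 1.9%; 5.7/150 = 3.8% |
| Interim trigger | 28.6% in one arm, 4.8% in the other, highest case | about 18 | 18/300 = 6%; 18/150 = 12% |
| Interim trigger | 28.6% in both arms, highest case | 26.8 | 26.8/300 = 8.9%; 26.8/150 = 17.9% |

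The two denominators arise because 300 twins may mean 300 pregnancies or 300 infants from 150 pregnancies. The count is the same at either point because it depends on the delivery rate and length of stay, not on how many have already delivered. The 4.8% is the pessary group of the same study; births before 37 weeks in that arm were taken as 50 to 56.6% (assumed).

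These are upper counts. An item already met is not lost, and the model ignores deaths and gives very early births a full stay.

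**3. Cut-offs in completed days**

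| Label | Label means day < | Definition says day < | Day excluded |
|---|---|---|---|
| 37 weeks | 259 | 258 | 36+6 |
| 34 weeks | 238 | 237 | 33+6 |
| 32 weeks (three outcomes) | 224 | 223 | 31+6 |
| 30 weeks | 210 | 209 | 29+6 |
| 28 weeks | 196 | 195 | 27+6 |

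That is seven definitions, each one day short. The test table and interim list in 9.1 use the labels (34 weeks for birth, 32 weeks for membrane rupture and hospitalisation), so they include the day that 4.1.2 leaves out. The documents give no daily distribution of births, so the number of women affected cannot be computed.

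**The case against.** - **The interim text is only a trigger.** Unlike the secondary analysis, the interim carries no instruction to analyse at once, and applying the 4.1.2 definition of morbidity already implies waiting for discharge. This stands, so the interim point is a clarification.
- **The explicit timing error has almost no effect.** It touches under 0.5% of pregnancies, and the remark about follow-up to birth mainly explains why dropout is expected only for the three-year outcome. This stands as to size. The text still contradicts itself in two places.
- **The cut-offs are editorial.** The labels are clear, and section 2.2 writes its strata as inclusive ranges (16+0 to 19+6), so the authors may have meant up to and including 36+6 and so on. This is likely. But the word before is used each time, and a literal reading gives a different rate.
- **The highest interim figure is a worst case.** It applies a comparison-group rate to both arms. This stands, and 6 to 18 is the fairer range.

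A reader might infer three stronger things:
- *The interim rule would stop the trial on biased data.* The documents do not say that data are taken at the trigger, and the direction of any distortion is unknown.
- *The one-day cut biases the comparison.* The same cut applies to both arms, so nothing in the documents shows this.
- *The 24-hour limit on neonatal death in 4.1.2 is a further error.* It is a choice of window, and later deaths count in the primary outcome, survival to age 3.

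**Conclusion.** Two statements are wrong as written, both minor and both confined to secondary outcomes and the interim items that share their definitions.

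1. Secondary data are not complete at the last delivery. The literal effect is about 0 to 3 of 672 pregnancies, given the assumed recruitment period, delivery-age distribution and discharge ages.
2. Seven definitions each exclude one day that their label includes. Rates are slightly lowered and mislabelled, not clearly biased.

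The missing interim data cut is a related gap. If data were taken at the trigger, about 6 to 18 pregnancies would have infants in hospital, and up to 27 only if the 28.6% rate held in both arms. The primary outcome, its timing and the sample size do not change.

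**What to change.** **Secondary analysis (9.1).** Set time point (1) at discharge or death of the last infant after all enrolled women have delivered, and delete the remark that follow-up runs only to birth. Cost: the analysis moves by some weeks.

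**Interim (9.1).** Keep the trigger and say whether it counts pregnancies or infants. State that discharge-based items are analysed once the included infants are discharged or have died, or at a stated maximum follow-up. Also state whether the birth-based tests may be acted on first.

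The downside is a wait for the discharge-based items. Assuming discharge at 40 weeks and recruitment still running over 24 or 30 months (730.5 or 913 days):
- Birth at 28+0 on the trigger day: 12 weeks. 84 × 672/913 = 62 to 84 × 672/730.5 = 77 more women enrolled.
- Birth at 24+0: 16 weeks. 112 × 672/913 = 82 to 112 × 672/730.5 = 103 more women enrolled.

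A maximum follow-up would limit this wait.

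**Cut-offs (4.1.2).** Write before 37+0, 34+0, 32+0, 30+0 and 28+0 for the preterm-birth outcomes, and before 32+0 for membrane rupture and hospitalisation. Cost: wording only.

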Women attending the reference hospital due to cervical shortening in twin pregnancies and fulfil the entry criteria (dichorionic twin pregnancy with cervical shortening \leq 25th percentile and do not fulfil the exclusion criteria), the study will be proposed. The patients will be informed of the intended therapeutic effect and possible side effects. If they agree and after obtaining their informed consent, they will be randomised according to the respective gestational week to either usual management (=control group) or cervical pessary placement up to 37 weeks (=pessary group). According to the gestational week and when the cervical shortening is under the 25th percentile the patients will be randomized to the following subgroups: gestational age in weeks 16-20, gestational age in weeks 20-24 and gestational age in weeks 24-28.

Specifically, the 25th centile of cervical length is defined at 32 mm, 30 mm and 28 mm for the 16+0 – 19+6, 20+0 – 23+6 and 24+0 – 28+0 weeks of gestation respectively.

2.3. Name and description of the device under investigation.

The Arabin cervical pessary, which is CE-certified for preventing SPB (CE 0482 / EN ISO 13485: 2012 + AC:2012 annex III of the council directive 93/42 EEC).

See annex I.

2.4. Statement that testing will be performed according to protocol, GCP and applicable legal requirements.

The Clinical Trial will be conducted following the protocol, the GCP, and all legal requirements.

3. Objective

This study aims to investigate the benefit of placing a cervical pessary in comparison to the expectant standard management in dichorionic twin pregnancies with cervical shortening \leq 25 percentile in terms of long-term survival without neurodevelopmental disability of the children.

Hereby, a standardized validated test called 'Ages and Stages 3rd edition' should evaluate the children's neurodevelopment at the age of 3 years. The test can be conducted by the parents and takes approximately 12 minutes. The questionnaires will be provided by the sponsor.

4. Design

4.1. Specific description of primary and secondary variables.

4.1.1. Primary outcome:

- Children`s survival without neurodevelopmental disability at the age of 3.

4.1.2. Secondary outcomes:

[figure not shown]
- Offspring
 - Time to birth
 - Preterm birth before 37 weeks: rate of delivery before 36+6 weeks
 - Preterm birth before 34 weeks: rate of delivery before 33+6 weeks
 - Preterm birth before 32 weeks: rate of delivery before 31+6 weeks

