If a woman with a dichorionic twin pregnancy at a gestational age of 16 weeks up to 28 weeks is diagnosed with a shortened cervix \leq 25 percentile during a preventive examination in pregnancy her vaginal pH-value is checked to preclude a vaginal infection. If her pH-value is $< 4,4$ she will be informed about the ongoing trial. If she is willing to participate and gives her informed consent, the woman will be randomized according to her respective gestational age to either pessary treatment group or expectant management group.

If the pregnant woman is assigned to the pessary group the pessary will be inserted directly. This procedure does not need anaesthesia and it does not need to be done in a surgery room. After the insertion of the pessary the correct fit of the pessary is verified by transvaginal ultrasound and in case it does not fit perfectly, it can easily be adjusted. The pessary will be removed at 37 weeks of gestation, or before if any unexpected event occurs (see 4.6).

After insertion of the pessary the obstetrical management during the pregnancy will be the same in both groups. Further surveillance of the pregnancy will not be influenced by the participation on the study.

4.5. Expected duration of subject's participation.

Study calendar:

Starting recruitment: July 1st, 2018

Finishing recruitment and follow-up: Dec 31st, 2023

Final report: July 2024.

4.6. Completion and interruption criteria of the study or the subjects.

The pessary will be removed at 37+0 weeks of pregnancy. The indications to remove them before this time will be: active bleeding stronger than usual period bleeding, persistent contractions after tocolysis and premature rupture of the membranes after 34 weeks.

After removing the pessary, the obstetrical management will be done as usual and will not be influenced by the study.

4.7. Maintenance of the randomisation codes and test procedures of the trial.

Every participating centre will have its own randomisation list.

We have created a database in a website so it can be accessed worldwide, that every hospital will be able to randomize their patients.

Every center will receive a password and a username in order to access the database for recruitment, randomization and documentation of patient data. Hereby, a personal identification number will be assigned for every patient. Patient names will not appear in the databases.

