This database will be supervised and coordinated by PD [name], Bürgerhospital Frankfurt/M. (Webmaster).

4.8. Identification of data to be collected in the case report files (CRF) that should be considered as data source.

Data will be collected in E-CRF, provided by >[name] Wissenschaft, Berlin< on study software "Castor".

4.9. Definition of what is considered to be the end of the study.

The study will be finished after the 3 year-follow up examination concerning neurodevelopmental disabilities, which will be conducted on the surviving children of the participating patients.

5. Selection and withdrawal of subjects

5.1. Inclusion criteria.

- Dichorionic diamnionic twin pregnancy with
- 16-28 weeks of gestation
- Minimal age of 18 years
- Informed consent signature

5.2. Exclusion criteria.

- Monochorionic twin pregnancy
- Major fetal abnormalities (requiring surgery or leading to infant death or severe handicap)
- Cerclage prior to randomisation
- Uterine malformation
- Placenta previa totalis
- Active vaginal bleeding at the moment of randomization
- Spontaneous rupture of membranes at the time of randomization
- Silicone allergy

- Current participation in other RCT
- Painful regular uterine contractions

5.3. Withdrawal criteria.

If a participant may voluntarily withdraw from treatment or if it is necessary to remove the pessary due to the conditions described before, the patients will be followed as usual until delivery (intention-to-treat analysis).

The death of one twin is not an exclusion criterion for the pessary placement.

The replacement of patients is not applicable in this trial.

5.4. Rescue treatment criteria.

If the cervical length decreases later on during the pregnancy, the management of the pregnancy in each centre will be the usual.

In case of secondary cervical shortening in the follow-up period pessary treatment may be offered as a rescue treatment up to 32+0 weeks of gestation.

Cervical cerclage or progesterone are generally not indicated in twin pregnancies.

6. Treatment of Subjects

6.1. Treatments to be administered.

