The pessary will be inserted during a preventive examination in pregnancy in the examination room. This procedure does not need anaesthesia and it does not need to be done in a surgery room. After the insertion of the pessary the correct fit of the pessary is verified by transvaginal ultrasound and in case it does not fit perfectly, it can easily be adjusted. The pessary will be removed at 37+0 weeks of gestation, or before if any unexpected event occurs (see 4.6).

After insertion of the pessary the obstetrical management during the pregnancy will be the same in both groups. Further surveillance of the pregnancy will not be influenced by the participation on the study.

7. Efficacy assessment

7.1. Specification of efficacy parameters: Primary and secondary endpoints.

This study aims to investigate the benefit of placing a prophylactic cervical pessary in comparison to the usual management in twin pregnancies with cervical shortening ≤ 25 percentile in terms of long-term survival without neurodevelopmental disability of the children.

7.2. Methods and timing to assess records and analyze the efficacy parameters.

The patients will be assessed according to usual management in a twin pregnancy.

	Regular preventive exam	Regular preventive exam	Postnatal evaluation	3 years follow up (corrected age)
Study procedure	study inclusion			
Informed consent	x			

Randomisation	x			
Pessary placement	x			
Pessary removal		x at 37 WoG		
physical exams				
Abdominal US	x	x		
Vaginal US	x Cervical length ≤ 25 percentile			
pH-Value	pH < 4,4			
Neonatal Examination			x	
Ages and stages test				x
Exam at paediatrician				x

8. Assessment of Safety

8.1. Procedures to record and report adverse events.

If a serious and unexpected adverse effect occurs during pessary treatment, it will be notified to the study Sponsor. The Department of Obstetrics and Gynecology of the Sponsor will fill the side effects document to notify it to the *Landesärztekammer Hessen*.

The patient affected by the adverse effect will be followed more intensively during the first days and if nothing else occurs, she will return to the standard control.

8.2. Definitions.

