Neonatal Morbidity	Cochran-Mantel-Haenszel-Test, Chi-Quadrat Test
Need for Hospitalization (mother)	Cochran-Mantel-Haenszel-Test, Chi-Quadrat Test
Days of Hospitalization (mother)	van Elteren Test, Wilcoxon-Mann-Whitney Test
Maternal Adverse Events	Cochran-Mantel-Haenszel-Test, Chi-Quadrat Test
Pessary Intolerance	Cochran-Mantel-Haenszel-Test, Chi-Quadrat Test
Vaginal Infections	Cochran-Mantel-Haenszel-Test, Chi-Quadrat Test

9.2. Expected number of subjects to be included.

For sample size calculation, we account for the stratified design and assume three equally large gestation groups. For the pessary group, we assume a combined event rate of at least 8% for the primary outcome and for the comparison of the pessary group with the control group we assume an odds ratio of 2.29. This odds ratio correspond to the lower bound of a one-sided confidence interval for the event rate given in van't Hooft (ProTwin Trial¹²). To reach a power of at least 80%, we have to evaluate at least 500 patients, 250 in the pessary group and 250 in the control group. To account for a drop out rate of 25%, overall n=672 pregnant women will be recruited.

9.3. Criteria for termination of the trial.

A non-justified case of maternal death (temporary stop until complete evaluation of the case by an external committee).

9.4. Selection of subjects to be included in each analysis.

The analysis will include all the subjects that have been randomised.

10. Direct Access to Data Source

Direct access will be granted to the authorized monitor, host institution and the regulatory authorities to permit trial-related monitoring, audits and inspections.

11. Quality and Control Assurance

Main investigator and collaborators: In order to ensure the Quality of the data they will provide instructions and training to the sites involved in the trial; review the CRF data; and detail of any other steps taken to ensure quality of research.

The main investigator will sign the study protocol and the “investigator’s commitment; he will apply for the Ethics Committee and the Director’s approval; and he will review the final report of the study.

The collaborators will assess patient’s eligibility, they will inform the patients and ask for the informed consent; and they will be responsible of the CRF and obtaining and registering all data.

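### The primary test is scheduled at 3 years corrected age, but the primary analysis is timed at 3 years from the last enrolled woman's delivery, so some late-enrolled children are not yet due at read-out

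*Combined protocol and SAP*

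**What the plan says.** **When the test is done.** The schedule table in section 7.2 is the only place that tells sites when to test. It puts the Ages and Stages test and the paediatric exam in a column headed "3 years follow up (corrected age" (closing bracket omitted). No section gives the reference week for the correction or a visit window.

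**How the endpoint is worded.** Section 4.1.1 defines it as "Children`s survival without neurodevelopmental disability at the age of 3". Section 3 says that the instrument "should evaluate the children's neurodevelopment at the age of 3 years". The synopsis uses the same kind of wording. None of the three says whether the age is corrected.

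**When the endpoint is analysed.** Section 9.1: "The primary outcome will be evaluated 3 years after the last woman enrolled in this study has delivered her twins".

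**Who is analysed.** Section 9.1 says that the primary outcome "will be analysed for all pregnancies with available primary endpoint". Section 9.4 says: "The analysis will include all the subjects that have been randomised".

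**When the study ends.** Section 4.9: "The study will be finished after the 3 year-follow up examination concerning neurodevelopmental disabilities".

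**The concern.** Three years corrected age is always later than the third birthday for a child born before its due date. Twins are usually born before it, and the pessary itself comes out at 37+0 weeks. An analysis fixed at three calendar years after a delivery therefore precedes the scheduled test for that woman's children. It also precedes it for other women whose due dates fall after the anchor date. The anchor is the delivery of the last woman *enrolled*, who need not be the last to deliver, because enrolment spans 16 to 28 weeks.

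Two things are at stake:

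- **Loss of endpoints.** Under the available-endpoint rule, a late pregnancy with a twin death already has its event, while one with two survivors awaiting the test has no endpoint. Late pregnancies would enter the primary test over-represented by events, and the evaluable number would fall.
- **Two possible test ages.** If a site read age 3 as chronological age in order to meet the read-out, developmental age at testing would depend on gestation at birth, which the pessary is meant to change. This is the secondary part of the point.

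**Working it through.** **1. The plan's own sample size.** Inputs from section 9.2: pessary event rate 8%, odds ratio 2.29, 80% power, 25% drop-out; two-sided alpha 0.05 from section 9.1.

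- Control rate = 2.29 × 0.08 / (0.92 + 2.29 × 0.08) = 0.1832 / 1.1032 = 0.166.
- The two-proportion normal formula gives 228 per arm without continuity correction and 251 with it. Power at 250 per arm is 83.6% and 80.0% respectively. The stated 250 per arm is reproduced with the correction.
- Drop-out: 500 / 0.75 = 667. Rounding up within 3 strata × 2 arms gives 500 / 6 → 84 per cell, 84 / 0.75 = 112, and 112 × 6 = 672, as stated.
- Expected evaluable: 672 × 0.75 = 504. The margin over 500 is 4 pregnancies.

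**2. Gap between third birthday and corrected age 3.** Correction to 40+0 weeks is an assumption. The gap is 40 − *g* weeks for birth at gestation *g*: 3 weeks at 37, 6 at 34, 8 at 32 and 12 at 28.

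**3. Who is not yet due at read-out.** Corrected age 3 = birth + (40 − *g*) weeks + 3 years = due date + 3 years. For a woman enrolled on date *e* at gestation *a*, the due date is *e* + (40 − *a*) weeks. If the last woman enrolled joins on date *L* at gestation *a_L* and delivers at *g_L*, the anchor is *L* + (*g_L* − *a_L*) weeks. A pregnancy is undue when

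*e* + 40 − *a* > *L* + *g_L* − *a_L*.

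Its own gestation at birth does not appear. Only enrolment date and gestation at enrolment matter, plus the anchor pregnancy.

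Example: the last woman enrols at 26 weeks and delivers at 36, so the anchor is *L* + 10 weeks. Women enrolled at 16 weeks are due at *e* + 24, so they are undue if enrolled within 24 − 10 = 14 weeks of *L*. Women enrolled at 28 weeks are due at *e* + 12, so they are undue only if enrolled within 2 weeks of *L*. The undue pregnancies are therefore mainly early-gestation enrolments.

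**4. How many.** I simulated 672 pregnancies. Assumptions not in the documents: uniform accrual, and delivery gestation centred on 36 weeks for 85% and on 28 weeks for 15%. Enrolment was in equal thirds across the strata, as section 9.2 assumes.

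The calendar does not fix accrual length. Recruitment starts on 1 July 2018 ("Starting recruitment: July 1st, 2018") and recruitment and follow-up end on 31 December 2023. Three chronological years need the last delivery by 31 December 2020, about week 131. Enrolment at 16 weeks and delivery at 37 takes 21 weeks, leaving about 131 − 21 = 110 weeks. I also used 156 and 260 weeks. Evaluable N = 504 − 0.75 × undue; power is continuity-corrected.

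| Anchor | Accrual (weeks) | Mean undue (5th-95th percentile) | Share of 672 | Evaluable | Power |
|---|---|---|---|---|---|
| Last woman enrolled | 110 | 34.4 (5-81) | 5.1% | 478 | 78.0% |
| Last woman enrolled | 156 | 25.0 (3-57) | 3.7% | 485 | 78.7% |
| Last woman enrolled | 260 | 15.5 (2-37) | 2.3% | 492 | 79.3% |
| Last delivery in trial | 110 | 7.6 (2-15) | 1.1% | 498 | 79.8% |
| Last delivery in trial | 156 | 6.5 (2-12) | 1.0% | 499 | 79.9% |
| Last delivery in trial | 260 | 5.1 (1-10) | 0.8% | 500 | 80.0% |

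With the literal anchor, about 6 to 15 of the undue pregnancies have not even delivered on the anchor date. The percentile range is wide because the anchor rests on one woman. At its top, 81 undue would leave 504 − 0.75 × 81 = 443. The evaluable figures treat every undue pregnancy as lost and so are slightly pessimistic, since those with a twin death keep an endpoint.

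**5. By gestation at birth** (literal anchor, 110 weeks). The chance of being undue is 5.9% for births before 28 weeks and 5.1% in each of the bands 28-32, 32-36 and 36 or more. Births before 32 weeks are 13.5% of undue pregnancies and 12.7% of all.

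**6. Chronological reading.** A child tested on its third birthday is developmentally 12 weeks younger than 3 years if born at 28 weeks, and 3 weeks younger if born at 37.

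**The case against.** **The plan may intend to wait.** Section 4.9 ends the study only after the 3-year examinations of the surviving children. Section 9.1 sets no data-lock rule and does not say that pending children are dropped; it links missing primary data to drop-out over long follow-up. This is fair, and it makes the loss avoidable in practice. But section 4.9 does not change the analysis date in section 9.1, and that date cannot be met with the schedule in section 7.2.

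**Age 3 may be shorthand.** The one operational schedule says corrected age, and no section says chronological. That stands, so the chronological reading is a risk and not the plan's stated rule. Whether it would lower scores also depends on the instrument's age bands and scoring, which the documents do not give.

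**The size is small.** That stands too.

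**A stronger reading to avoid.** A reader might infer that the most preterm children are caught disproportionately, because their wait after the third birthday is longest, so that outcomes are removed where disability concentrates. The documents do not support this. An earlier birth also brings the third birthday forward by the same amount. The two cancel, and the due date is fixed before randomisation. Dividing the wait at each gestation by the accrual period would produce a steep gradient, but only by ignoring that cancellation.

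**Conclusion.** The inconsistency is real, and the stated rule fails when followed: the analysis date in section 9.1 falls before the scheduled test for some surviving children. With correction to 40+0 weeks, even accrual over about 2 to 5 years and the assumed delivery distribution, on average 2-5% of pregnancies are undue with the anchor as written, and about 1% with the last delivery in the trial. The cost is at most about 2 points of power on average, but it takes the expected evaluable number below 500 because the plan's margin is only 4.

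The missing endpoints are informative within late enrolments, since deaths count and pending survivors do not. This applies in both arms, so it does not by itself show a bias in the comparison. Dependence on gestation at birth arises only if age 3 is applied chronologically, and that remains a secondary concern. The point merits an amendment because it concerns the timing of the primary endpoint and is cheap to settle.

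**What to change.** - Use 3 years corrected age, with its reference week and a test window, as the single time point in the synopsis and sections 3, 4.1.1, 4.9 and 9.1, matching section 7.2.
- Replace the trigger in section 9.1 with the date on which every surviving child has completed or passed that window, that is, the latest expected due date plus 3 years plus the window.
- State that children not yet due are awaited and are not counted as unavailable.
- Check the study calendar against the new trigger. With corrected age, the last due date (and not only the last delivery) would have to fall by 31 December 2020 for follow-up to end on 31 December 2023, before adding the window.

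The cost is a wording amendment. Read-out moves later by about 9 weeks on average with the anchor as written, or about 4 weeks if it was meant to be the last delivery in the trial, plus the window. No child is then undue, and the planned 504 evaluable pregnancies and about 80% power are kept.
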